## ii. List of Abbreviations

ABG	Arterial blood gas
AE	Adverse Event
AF	Atrial Fibrillation
AHRF	Acute hypercapnic respiratory failure
APACHE II	Acute Physiology and Chronic Health Evaluation II
CCI	Charlson Comorbidity Index
CI	Chief investigator
COPD	Chronic Obstructive Pulmonary Disease
CPAP	Continuous Positive Airway Pressure
DECAF	Dyspnoea, Eosinopenia, Consolidation, Acidaemia and atrial Fibrillation
DLOAI	prognostic score
DMC	Data Monitoring Committee
ECOPD	Exacerbation of Chronic Obstructive Pulmonary Disease
eMRCD	Extended Medical Research Council Dyspnoea
EPAP	Expiratory positive airway pressure
HADS	Hospital anxiety and depression scale
HCO 3 -	Bicarbonate
HRA	Health Research Authority
IPAP	
kPa	Inspiratory positive airway pressure
	Kilopascal
NHS	National Health Service
NIHR	National Institute for Health and Care Research
NIV	Non-Invasive Ventilation
NIVO	Non-Invasive Ventilation Outcomes
PaCO 2	Partial pressure of carbon dioxide in arterial blood
PEARL	Previous admissions, eMRCD score, Age, Right-sided heart failure and
DEED	Left sided heart failure
PEEP	Positive end-expiratory pressure
PI	Principle investigator
PPI	Patient and public involvement
PS Pt-CO	Pressure support
PtcCO 2	Transcutaneous carbon dioxide
RCT	Randomised controlled trial
REC	Research Ethics Committee
RfPB	Research for Patient Benefit
SAE	Serious Adverse Event
SGRQ-C	St Georges Respiratory Questionnaire for COPD
SpO 2	Oxygen saturation
TMG	Trial Management Group
TSC	Trial Steering Committee
UK	United Kingdom
VAS	Visual analogue scale

IRAS: 313485 CPMS: 53277

## iii. Trial Summary

Trial Title	Standard versus accelerated weaning from (NIV) in chronic obstructive pulmonary doutcomes score: a randomised controlle	lisease directed by the NIV
Short Title	Non-Invasive Ventilation Outcomes score-directed Weaning (NIVOW)	
Trial Design	A multi-centre, open-label, parallel, randomised controlled trial.	
Trial Participants	Clinical diagnosis of ECOPD complicate PaCO 2 >6.5kPa), with low or medium risl meeting criteria for weaning.	d by AHRF (pH<7.35 and
Planned Sample Size	164 participants randomised.	
Treatment Duration	24 months of recruitment.	
Follow Up Duration	90-days follow up post-randomisation.	
Planned Trial Period	Recruitment 01/09/2022 to 31/08/2024.	
	Objectives	Outcome Measures
Primary	To compare time to successful weaning from NIV in ECOPD using an accelerated versus a standard weaning protocol.	Time to successful weaning.
Secondary	To compare relapse requiring NIV (defined as recurrent AHRF>48 hours after removal of the ventilator), complications of NIV, respiratory symptoms (breathlessness and sputum clearance), sleep quality, health-related quality of life, readmissions, mortality, and NHS cost and cost-effectiveness between both weaning strategies.	Relapse requiring NIV; Total duration of ventilation; Length of hospital stay; NIV complications; Patient reported outcome measures; Mortality; Readmissions; Health economic analysis; Responder analysis (accelerated weaning group).
Control Arm	Standard weaning protocol: Progressive determined by arterial blood gas (or cap	
Intervention Arm	Accelerated weaning protocol: Daily 4-hour weaning trial, success confirmed by arterial blood gas, with additional transcutaneous carbon dioxide monitoring.	

ISRCTN: 64639614 IRAS: 313485 CPMS: 53277

## v. Role of Trial Sponsor and Funder

Sponsor	The Sponsor, Northumbria Healthcare Foundation Trust, assumes overall responsibility for the initiation and management of the trial.
Funder	The trial funder, NIHR (RfPB), undertook independent peer review of the trial proposal. They will not be directly involved in the trial design, conduct, data analysis and interpretation, manuscript writing, and dissemination of results.

# vi. Roles and Responsibilities of Trial Management Committees, Groups and Individuals

Trial Steering Committee	A Trial Steering Committee will be formed with an independent Chair, and will meet at least every six months, and send timely reports to the Sponsor. The independent Chair is: [name] Consultant Respiratory Physician [contact]
Data Monitoring and	Email: [contact]  A Data Monitoring and Ethics Committee will be formed with an
Ethics Committee	independent Chair, and will meet at least every six months, and report to the Trial Steering Committee. The Committee members will be completely uninvolved in the running of the trial. The independent chair is:  [name]  Consultant Respiratory Physician  [contact]  Email: [contact]
Trial Management Group	The Trial Management Group will meet regularly to ensure all practical details of the trial are progressing and working well, and everyone within the trial understands them. The Chair will be the Chief Investigator who assumes primary responsibility for the design, conduct and reporting of the trial. Chief Investigator:  [name] Consultant Respiratory Physician [contact] Email: [contact]

IRAS: 313485 CPMS: 53277

[figure not shown]

## viii. Key Words

Non-Invasive Ventilation	Ventilation delivered via a face mask connected to a
(NIV)	ventilator to help patients to breathe out a build-up of the
	waste gas carbon dioxide.
Chronic Obstructive	A lung disease causing breathlessness, sputum production
Pulmonary Disease	and frequent flare-ups (exacerbations).
(COPD)	
Acute Hypercapnic	Respiratory acidaemia diagnosed via arterial blood gas
Respiratory Failure	(quantified by pH<7.35 and PaCO 2 (carbon dioxide) >6.0kPa.
(AHRF)	
NIV Outcomes Score	A clinical risk stratification tool to predict mortality in patients
(NIVO score)	with exacerbation of COPD complicated by AHRF and
	requiring NIV treatment.
Standard weaning versus	Patients will be randomised between these two weaning
accelerated weaning	protocols, standard weaning and accelerated weaning.
Time to successful	Duration from the baseline arterial blood gas confirming
weaning	selection criteria is met, to final removal of the ventilator.

IRAS: 313485 CPMS: 53277

#### 1. Background

One quarter of patients admitted to hospital with exacerbation of Chronic Obstructive Pulmonary Disease (ECOPD) are complicated by life-threatening respiratory acidaemia/acute hypercapnic respiratory failure (AHRF).

AHRF results from the inability of the respiratory system to maintain sufficient alveolar ventilation to keep arterial carbon dioxide (PaCO2) and pH within normal limits. If respiratory acidaemia persists despite initial medical therapy, non-invasive ventilation (NIV) is the treatment of choice.

Weaning refers to how ventilation is discontinued once a patient has improved on treatment. Current British Thoracic Society (BTS) guidelines recommend withdrawal of NIV over 4 days, but this is not based on randomised controlled trials (RCTs) comparing different weaning strategies. Reducing the duration of NIV, i.e. faster weaning, should reduce side-effects and complications for patients, as well as costs to the National Health Service (NHS). However, shorter treatment may be less effective, and respiratory failure (carbon dioxide build-up) may recur. The most effective way to wean NIV is unclear, and patients and clinicians have identified this as a research priority.

There have been 4 RCTs comparing different strategies to wean patients with ECOPD from NIV. There are no planned or current registered trials similar to our proposed RCT.

Duan et al (2012) compared protocol-directed (n=37) and physician-directed (n=36) weaning from NIV. Protocol directed weaning included once daily unsupported breathing trials once specific clinical criteria were met, repeated until successful. This was associated with a shorter mean duration of NIV, 2.6 versus 4.4 days (p<0.001), and duration of ICU stay, 5.8 versus 8.1 days (p=0.02). This trial supports protocol-directed weaning, but was small and included patients with a range of conditions (COPD=47/73).

Two small RCTs compared a single attempt at immediate NIV withdrawal to a stepwise approach, but they were underpowered to detect a meaningful clinically significant difference. Success, defined as the absence of recurrent AHRF within 48 hrs, was not statistically different. Lun: immediate=14/25, stepwise=26/35; Venkatnarayan: immediate=23/30, stepwise reduction in pressures=27/30, stepwise reduction in duration=26/30. More importantly, failure of a first daily trial of unsupported breathing does not mean that the patient has failed to wean from NIV; repeated weaning trials should be performed on subsequent days.

Sellares compared direct discontinuation of NIV (if initially unsuccessful, further attempts were performed) to nocturnal NIV for three additional nights once AHRF had resolved. Relapse with recurrent AHRF within 8 days of weaning occurred in: direct discontinuation group=10/59; nocturnal NIV group=8/61. Length of stay on the respiratory critical care unit was shorter with direct discontinuation. There were no significant differences in other outcomes. There was an unexplained 3.5-year hiatus during recruitment. In comparison to this study, recent large UK cohorts show more severe AHRF. Across UK national audits, patients with progressively more severe AHRF were managed with NIV.

ECOPD is the most common condition treated with NIV. Current guidelines on NIV weaning are not based on robust evidence, and are inconsistently followed. The NCEPOD report into NIV outcomes highlights serious concerns that this research will help to address.

We recently developed the NIV Outcomes Score, that uses risk-stratification to accurately predict in-hospital mortality in patients with ECOPD requiring NIV.9 Previous randomised controlled trials (RCTs) assessing accelerated NIV weaning protocols did not use objective prognostic tools to select patients.

This trial will clarify whether risk stratification can facilitate quicker weaning from acute NIV in patients with low and medium mortality risk. It will assess outcomes important to patients, and help address the marked variation in clinical practice.

#### 2. Rationale

Despite NIV being one of the most effective interventions for ECOPD complicated by AHRF, it can cause complications and unpleasant side-effects for patients, including pressure areas from the face mask, and gastric distension and hypotension from the pressure delivered. A shorter duration of weaning from the ventilator should provide benefits to patients and reduce costs to the NHS.

In addition, consecutive national audits raised concerns about UK NIV services, triggering a National Confidential Enquiry into Patient Outcome and Death (NCEPOD). Mortality in patients with ECOPD was 25.1%, compared to around 10% in clinical trials. NIV provision, including weaning strategies, varied considerably across hospitals.

Previous randomised controlled trials (RCTs) assessing accelerated NIV weaning protocols did not use objective prognostic tools to select patients. In the absence of a robust prognostic tool, they excluded patients with various features thought to confer high risk of poor outcome, notably co-existent consolidation.

We recently developed the NIV Outcomes (NIVO) score, to accurately predict in-hospital mortality in patients with ECOPD requiring NIV. There was marked variation in duration of ventilation (31.5 to 95.5 hours) and relapse (4.5 to 15%) across the 10 centres involved, highlighting the need for objective guidance.

Using the NIVO score, 75% of patients have a low or medium mortality-risk and therefore may be suitable for accelerated weaning. The score is calculated using readily available clinical indices:

NIVO Score	Points
Chest radiograph consolidation	1
Glasgow Coma Scale (GCS) <15	1
Atrial Fibrillation (AF) including persistent, new or paroxysmal AF)	1
pH <7.25	1
Time to respiratory acidaemia >12 hours	2
Extended Medical Research Council Dyspnoea Scale (eMRCD) score 5a*	2
Extended Medical Research Council Dyspnoea Scale (eMRCD) score 5b*	3
Total	, _
	/ 9

\*The extended MRC Dyspnoea Score (eMRCD) is based on performance on a good day within the last 3 months.

5a = unable to leave their home unassisted, independent in washing and/or dressing.

5b = unable to leave their home unassisted and requires help washing and dressing.

Patients are scored as either eMRCD 5a or 5b.

Use of the NIVO score to select patients will broaden inclusion compared to previous weaning trials, whilst also ensuring optimal risk-assessment. The British Thoracic Society is including the NIVO score in the next national NIV audit, which will help to embed use of the NIVO score into routine practice across the UK.

This interventional randomised controlled trial will compare 2 weaning strategies, standard weaning and accelerated weaning, for patients with low and medium risk NIVO score.

Our standard weaning protocol reflects the current national guideline, advising that time on NIV should be maximised in the first 24 hours and tapered over the following 2 to 3 days, depending on pCO2 self-ventilating, before being discontinued overnight. We acknowledge that few clinical trials have been performed comparing weaning strategies/protocols in acute NIV, and whilst in some centres there is a very consistent approach to NIV weaning, this is not the case in all. [name] led the 10-centre validation study for the NIV Outcome score. Duration of NIV treatment was captured; we are therefore uniquely placed to ensure we select centres with a consistent approach (this was true of most, but not all, participating centres).

In regard to the accelerated weaning protocol, the Sellares study trialled 4 hours of unassisted breathing before discontinuation of NIV, and allowed most patients to be successfully weaned. We have considered the strengths and weaknesses of this small RCT, but it provides a published evidence base to support a more robust evaluation of this approach. In our clinical practice, we encounter some patients who strongly dislike acute NIV and ask to discontinue treatment early. We have anecdotally found that in those who are able to manage for at least 4-hours off NIV, an accelerated wean was more likely to succeed. The accelerated weaning protocol, including the 4-hour trial off NIV, was developed informed by both the available trial evidence and our clinical experience. We highlight that our overall outcomes are very favourable: inpatient mortality for COPD requiring NIV = 9.2% compared to 25.1% in the contemporaneous National Confidential Enquiry into Patient Outcome and Death.

It is essential that participating centres confirm that their service will support adherence to the assigned protocol. This reassurance is in place for the recruiting centres, having been confirmed by the respective Pl's.

Our recent Patient and Public Involvement (PPI) engagement confirms that patients would welcome a shorter period of NIV treatment, provided this remains safe and effective. This trial design has been developed with support from the Northumbria Lung Research PPI group and representative patients with low and medium risk NIVO score who have received acute NIV treatment. Separately, both patients and clinicians have identified NIV weaning as a research priority. A shorter stay on Critical Care or Respiratory Support Units would reduce NHS costs, with additional savings if overall length of hospital stay is shorter.

The hypothesis is that daily four-hour unsupported breathing trials, with removal of NIV if the patient remains clinically and physiologically stable, will shorten the time to successful wean from NIV, compared to the standard protocol in ECOPD with a low or medium mortality risk.

ISRCTN: 64639614 IRAS: 313485 CPMS: 53277

## 3. Objectives and Outcome Measures/Endpoints

#### 3.1 Primary aim

To compare time to successful weaning from NIV in ECOPD using an accelerated versus a standard weaning protocol.

#### 3.2 Secondary aims

To compare relapse requiring NIV (defined as recurrent AHRF>48 hours after removal of the ventilator), complications of NIV, respiratory symptoms (breathlessness and sputum clearance), sleep quality, health-related quality of life, readmissions, mortality, and NHS cost and cost-effectiveness between both weaning strategies.

#### 3.3 Primary outcome

Time to successful weaning: duration from the baseline ABG confirming selection criteria are met, to final removal of the ventilator. Weaning will be considered successful when there has been no recurrence of AHRF requiring replacement of NIV within 48 hours of discontinuation of NIV. Recurrent AHRF more than 48 hours after removal of the ventilator will be considered relapse. Death precludes weaning and will be captured in a competing risk analysis.

#### 3.4 Secondary outcomes

- 1. Relapse requiring NIV (defined as recurrent AHRF>48 hours after removal of ventilator).
- 2. Total duration of ventilation.
- 3. Length of hospital stay.
- 4. NIV complications (incidence and severity).
- 5. Patient reported outcome measures: Modified Borg dyspnoea scale\*; Sputum clearance via visual analogue scale\*; Richards-Campbell sleep questionnaire\*; Hospital Anxiety and Depression Scale (HADS) pre-discharge; St Georges Respiratory Questionnaire for COPD (SGRQ-C) and EQ-5D-5L days 7, 30 and 90 post-randomisations.
- 6. Mortality in-hospital and 90-days post-randomisation.
- 7. Readmissions 30-days post-discharge.
- 8. Health economic analysis:
  - Costs to the NHS in terms of provision of the interventions (both on a respiratory support unit and a critical care unit) and cost implications of subsequent resource utilisation up to 90 days follow up;
  - Cost utility analysis using EQ-5D-5L quality adjusted life years (QALYs).
- 9. Responder analysis within the accelerated weaning group to identify predictors of success/failure.
- \*Day 1 to 5.

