### 4. Trial Design

A multi-centre, open-label, parallel, randomised controlled trial.

Our position is one of equipoise. The randomised controlled trial design will provide a definitive result as to the better outcome for patients: a) a standard wean may provide a longer duration of NIV wean, with lower PaCO2 at discharge, with less relapse and readmissions; or b) an accelerated wean may mean a shorter duration of NIV wean, but with more relapse requiring NIV, and more readmissions.

IRAS: 313485 CPMS: 53277

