#### 7.10 Withdrawal Criteria

Participants are free to withdraw from the trial at any time without giving explanation. Date and time of withdrawal will be recorded on the source document worksheet by the usual care team. In this instance, there will be no further collection of patient reported outcome measures or spirometry testing, but we will continue to collect healthcare utilisation data and mortality until 90 days post randomisation (unless the participant states otherwise). Participants who have withdrawn from the trial after meeting the primary outcome (fully weaned from NIV including no relapse within 48 hours of removal of NIV) will not be replaced.

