#### 8. Trial Treatments

#### 8.1 Control Arm: Standard weaning

During weaning, arterial blood gases are performed at the end of a period off NIV to help direct the duration of subsequent breaks from NIV. ABG's can be performed at each stage of the standard (stepwise) weaning protocol, and if satisfactory, the participant can receive progressively longer intervals without NIV. Typically, at least one ABG is performed daily to determine the amount of time off NIV each day. An ABG may be omitted, if a justified clinical improvement is observed that allows progress to the next weaning step. More than one weaning step may happen in a day. Once the patient has managed a full day without support, they receive a final night on NIV. When NIV is discontinued the following morning, PtcCO2 monitoring is applied to the patient for 12 hours. Provided the patient remains stable, NIV will not be replaced.

The weaning time endpoint is the date and time that the NIV mask is removed from the patient's face for the last time (provided NIV does not need to be recommenced within 48 hours). Perform an ABG within 4 to 24 hours after the NIV mask is removed for the final time.

ISRCTN: 64639614 IRAS: 313485 CPMS: 53277

Some centres include a period of standby NIV after weaning, when the ventilator is kept at the bedside, with a subsequent ABG after 24 hours off NIV to confirm safe removal of the ventilator. This is entirely acceptable, but is not included in the weaning time.

Medical treatment will be optimised before and during NIV treatment. NIV will be delivered in spontaneous/timed pressure support mode. Supplementary oxygen will be strictly titrated to maintain  $SpO_2$  88-92% when on and off NIV (ideally controlled oxygen off NIV).

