#### For the outcome of the ABG:

pH≥7.35, leave the patient off NIV, continue PtcCO2 monitoring for a further 8 hours. If there are no signs of substantial clinical deterioration, and the PtcCO2 does not rise by >1kPa, then the ventilator and PtcCO2 monitoring can be removed from the bed space.

pH<7.35, replace the NIV mask on the patient and recommence ventilation, and repeat a 4-hour weaning trial the next day. 4-hour weaning trials are completed daily until successful.

An ABG should be performed during the 4-hour trial after NIV removal or during the 8-hour monitoring after a successful ABG if: 1) PtcCO2 rises by >1kPa, or 2) there is clinical concern, but any transient reasons for deterioration (e.g. coughing, mucus plugging) should be addressed first.

The weaning time endpoint is the date and time that the ABG is taken that confirms the first successful 4 hour weaning trial (provided NIV does not need to be recommenced within 48 hours).

Medical treatment will be optimised before and during NIV treatment. NIV will be delivered in spontaneous/timed pressure support mode. Supplementary oxygen will be strictly titrated to maintain  $SpO_2$  88-92% when on and off NIV (ideally controlled oxygen off NIV).

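### Patients put back on NIV within 48 hours of a declared wean are not counted by arm in any outcome; they appear only as added weaning time

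*Protocol*

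**What the plan says.** The protocol splits recurrence at 48 hours.

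- **Up to 48 hours.** Section 3.3: "Weaning will be considered successful when there has been no recurrence of AHRF requiring replacement of NIV within 48 hours of discontinuation of NIV". Sections 8.1 and 8.2 put the same condition on each arm's endpoint. Section 8.1 takes the last removal of the mask, "provided NIV does not need to be recommenced within 48 hours". Section 8.2 says "The weaning time endpoint is the date and time that the ABG is taken that confirms the first successful 4 hour weaning trial", with the same proviso.
- **After 48 hours.** Section 3.3: "Recurrent AHRF more than 48 hours after removal of the ventilator will be considered relapse". Sections 3.2 and 3.4 repeat this, and section 3.4 makes it the first secondary outcome: "Relapse requiring NIV (defined as recurrent AHRF>48 hours after removal of ventilator".

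Section 4 states one side of the equipoise as "an accelerated wean may mean a shorter duration of NIV wean, but with more relapse requiring NIV, and more readmissions".

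Section 7.10, on withdrawals, describes a patient who has met the primary outcome as fully weaned, "including no relapse within 48 hours of removal of NIV". There the word relapse covers the window that sections 3.2 to 3.4 exclude from it.

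**The concern.** The trial asks whether a faster wean is bought with more recurrent respiratory failure. A reader will look to the relapse outcome for that answer, and it omits the first 48 hours after NIV is stopped.

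That window matters because the arms enter it differently. Under section 8.1 a standard-arm patient has already managed a full day off NIV, followed by a last night on it. Under section 8.2 an accelerated-arm patient stays off after one satisfactory 4-hour trial. The first night without NIV falls inside the window in both arms, but for the accelerated patient so does the first full day.

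At stake is the safety half of the conclusion. A report of faster weaning with no more relapse could be correct under the definitions and still not show that more patients were taken off NIV and had to go back on.

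**Working it through.** **1. The plan's own figures.** Section 10.1 gives cumulative incidences of weaning of 0.50 and 0.667 at 2.71 days, with death at 0.054 in both arms.

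- Exponential times give the second incidence from the medians: 1 − 0.5^(2.71/1.71) = 0.667.
- Total hazard is −ln(1 − F − Fc)/t, split in the ratio F:Fc. The weaning hazards are 0.2689 and 0.4358 per day, a ratio of 1.62.
- Schoenfeld events: 4 × (1.960 + 0.842)² / (ln 1.62)² = 135. The plan has 67 + 69 = 136.
- Eventual weaning probabilities of 0.903 and 0.925 give 135/0.914 = 148 patients. Dividing by 0.9 for dropout gives 165, against 164 stated.

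The sample size reproduces and is not in dispute.

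**2. Where a restart of NIV is recorded.**

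| Restart after a declared wean | Primary outcome | Relapse outcome | Count by arm |
|---|---|---|---|
| Up to 48 h | Time runs on to a later wean | Not counted | None |
| After 48 h | Wean stands | Counted | Yes |

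Of the other secondary outcomes in section 3.4, total duration of ventilation probably absorbs an early restart, and length of stay may. NIV complications are described in section 2 as effects of the mask and the pressure, not as recurrent respiratory failure. The responder analysis looks at success and failure inside the accelerated arm only.

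**3. Can the primary outcome favour accelerated weaning despite more early restarts?** Assume exponential times with the planned accelerated median of 1.71 days before any added failures, so λ = ln 2/1.71 = 0.4053. Let an extra proportion p of accelerated patients fail early and lose d days each. When the median exceeds d, it equals 1.71 + ln(1 − p + p·e^(λd))/λ.

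| Extra early failures p | d = 1 day | d = 2 days |
|---|---|---|
| 10% | 1.83 | 2.00 |
| 20% | 1.95 | 2.26 |
| 30% | 2.05 | 2.50 |

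For example, p = 0.2 and d = 2 gives 1.71 + ln(0.8 + 0.2 × 2.249)/0.4053 = 1.71 + 0.55 = 2.26. All six values stay below the control median of 2.71 days. The values of p and d are assumptions; the protocol gives neither.

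**4. What the cited trials offer.** Section 1 gives 48-hour successes for two trials of immediate withdrawal. Subtracting from the group sizes:

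- Pilot trial ("immediate=14/25, stepwise=26/35"): failures 11/25 = 44.0% against 9/35 = 25.7%.
- Three-arm trial: 7/30 = 23.3% against (3 + 4)/(30 + 30) = 7/60 = 11.7%.

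Both point to more early failure with immediate withdrawal. Section 1 says the differences were not statistically significant. In the trial on which section 2 bases the 4-hour approach, recurrence within 8 days was 10/59 = 16.9% against 8/61 = 13.1%, a gap of 3.8 points.

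**5. Precision with 82 per arm.** The 95% half-width for a risk difference is 1.96 × √[(p₀(1 − p₀) + p₁(1 − p₁))/82]. For 10% against 20% it is 10.8 points, and for 10% against 30% it is 11.9. Two-sided 5% power is 69% at the pilot trial's rates and 50% at the three-arm trial's pooled rates.

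**The case against.** The best defence is that the split is deliberate and accounts for recurrence on both sides of 48 hours. An early recurrence is charged to the primary outcome, a late one to relapse, and section 10.3.3 analyses by intention to treat. That largely stands, and it rules out several stronger readings that a reader might infer.

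- *Early failures are not compared between arms.* They are, through time to successful weaning. What is missing is their frequency.
- *Early failure is the main expected harm.* Section 4 names relapse and readmissions, and section 1 says only that respiratory failure may recur. Nothing says that harm is expected mostly in the first 48 hours.
- *Relapse is analysed in a subset selected after randomisation.* No section limits the denominator to patients who got past 48 hours. A patient who fails early can wean later and then relapse.
- *The cited trials predict the number of hidden restarts.* Pooling the two immediate-withdrawal trials gives 18/55 against 16/95, which scales to about 27 against 14 per 82 patients. This does not carry over. Those trials used one attempt, and section 1 itself says that failing a first daily trial is not failing to wean. Under section 8.2 a patient with pH below 7.35 at 4 hours returns to NIV without having been declared weaned. The third trial shows a much smaller gap, over a different window.

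Section 7.10 is loose wording. Its substance agrees with section 3.3, so it needs correcting but is not evidence of bias.

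The defence does not meet one point. Added time does not substitute for a count, because a faster schedule can absorb the delays, as step 3 of the working shows.

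**Conclusion.** The point holds as a gap in reporting, not as an error in the primary outcome or the sample size. Recurrence requiring NIV within 48 hours enters the comparison only as added time in the primary outcome, and probably in total duration of ventilation. The relapse outcome excludes it, and no outcome gives its frequency by arm. The trade-off posed in section 4 would then be judged on a partial count of recurrences.

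The size is unknown. The median shifts rest on exponential times and on assumed failure rates and delays; they compare medians, whereas the planned test is a Fine-Gray model, and they ignore death. They show that masking is possible, not that it will occur. The two immediate-withdrawal trials are a loose illustration of direction only. The relapse outcome is not shown to be biased for what it defines; it is narrower than the question the trial poses.

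**What to change.** Keep the primary outcome and the relapse outcome after 48 hours as they are. Add to section 3.4 a between-arm secondary outcome: NIV recommenced for recurrent respiratory failure after it had been discontinued as weaned. Report it at up to 48 hours, after 48 hours and in total, over all randomised patients by intention to treat, with a risk difference and 95% CI. Present it as an estimate, not a powered test.

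The definition should exclude planned returns to NIV during standard weaning and returns after an unsuccessful 4-hour trial. It should also name the moment from which the 48 hours run in each arm, since section 3.3 refers to both discontinuation of NIV and removal of the ventilator, section 8.1 to mask removal, and section 8.2 to the confirming blood gas.

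Reconcile the word relapse in section 7.10 with sections 3.2 to 3.4.

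The cost is one more secondary outcome and a short amendment. Section 7.6 already collects NIV removal times and section 7.7 records NIV status daily. The primary outcome cannot be derived without knowing about restarts within 48 hours, so no new data or visits are needed and the sample size stays at 164.
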